16.6 Liability

The compensation and covered liability associated with this study conduct will be documented in a separate financial agreement signed by Medtronic, the PI, and/or the management of the study site/institution.

16.7 CIP Amendments

Protocol amendments may be initiated by Medtronic to address changes to the scope or conduct of the study. Protocol amendments, and associated documents, must be approved by Medtronic and submitted to the reviewing IRBs for approval prior to implementation except when necessary to eliminate an immediate or apparent immediate hazard to participating subjects.

16.8 Record Retention

16.8.1 Investigator Records

Documentation for this study will be produced and maintained to ensure that a complete history of the study exists. Documents created for this study, including all versions of original documents, will be identifiable and appropriately stored to assure control and traceability of data related to this study.

The PI is responsible for ensuring that all essential study documentation is retained and accessible for a minimum of 2 years (or longer as local law or facility administration requires) after the investigation is terminated or completed. The retention period may be longer if required by Medtronic, local or global regulatory requirements. Medtronic will be responsible for notifying sites of extensions to the 2-year minimum record retention requirements. Medtronic must be notified in writing by site personnel of any transfer of study documentation. The PI will ensure that essential study documents are not destroyed until written permission has been obtained from Medtronic or if allowed per contract.

At a minimum, the investigator is responsible for the preparation, review, submission to Medtronic and retention of all signed and dated case report forms, reportable adverse events, device deficiencies, subject deaths, deviations from the CIP. In addition, investigators are also responsible for maintaining all correspondence with another investigator, an IRB, the sponsor, a monitor, or FDA, related to this study (including approval documentation), records of each subject's case history and exposure to the device (including signed and dated informed consent forms & HIPAA authorizations, as well as source documentation of the consent process), final report, and all other study-related documentation.

16.8.2 Investigator Reports

The PI is responsible for the preparation (review and signature) and submission to the sponsor of all case report forms, adverse events, device deficiencies, deaths, and any deviations from the CIP. If any action is taken by an IRB with respect to this clinical study, copies of all pertinent documentation must be forwarded to Medtronic in a timely manner. Reports are subject to inspection and to the retention requirements as described above for investigator records.

Investigator reporting requirements for termination or suspension are listed in Section 16.10. The investigator shall prepare and submit in a complete, accurate and timely manner the reports listed in this section.

16.9 Publication and Use of Information

It is intended that study results will be published in scientific literature. Information provided related to patent applications, technical design, or manufacturing processes supplied to the investigator as a part of the investigational plan is considered confidential and is not to be included in publications without the consent of Medtronic. If required by a publisher, the PI agrees to obtain all necessary authorizations from study subjects prior to submitting study-related information for publication. Specific requirements regarding publication of study data will be provided in the study center agreement and in the publication strategy.

16.9.1 Publication Committee

Medtronic will form a publication committee to develop a publication strategy and to oversee the development and review of publications related to the study. The publication committee may include representation from physician study advisors, the designated participating investigators, and Medtronic. The publication committee will be responsible for overseeing and ensuring that the publication strategy is executed according to the established plan. Publication committee membership does not guarantee or provide privileges in terms of authorship.

The publication committee members will be responsible for reviewing all primary and secondary manuscripts prior to submission to the target journal and for reviewing abstracts prior to submission to conferences. In addition, publication committee members will review and approve requests for

secondary (ancillary) multicenter publications not included in the publication strategy. Requests will be reviewed to determine scientific validity, potential conflicts with previously submitted publications, and the need for Medtronic resources.

16.9.2 Authorship Selection

Authorship will follow the Ethical Considerations in the Conduct and Reporting of Research as defined by the International Committee of Medical Journal Editors (<http://www.icmje.org>).

16.10 Suspension or Early Termination

Early Termination is the closure of a clinical study that occurs prior to meeting defined endpoints. This is possible for the whole study or a single center. Suspension is a temporary postponement of study activities related to enrollment. This is possible for the whole study or a single center. Medtronic reserves the right to suspend or terminate the study or an individual study site at any time. In the event the study is terminated, the subject's devices will be programmed as per the investigator's discretion and once exited from the study, subjects will be managed by their physician.

16.10.1 Study-Wide Termination or Suspension

Medtronic reserves the right to suspend or terminate the study at any time. Reasons may include, but are not limited to, the following:

- Insufficient enrollment to complete the study within the expected timeframe
- Identification of adverse events or safety issues with the product or system that may impact the safety or welfare of study subjects
- Product performance/product supply issues

18.1 Appendix A: Additional Information for Sites

Detailed sponsor contact information not outlined in the Clinical Investigational Plan will be provided under a separate cover.

2.0	
Amendment 1 includes the following updates and clarifications:
 
patients using cannabinoids (including cannabidiol) are excluded from the studypatients must be on a minimum daily systemic opioid dose > 0 MME at the time of enrollment in the studypsychological evaluation to be conducted per standard of carepatient must have an MRI or CT and no clinical change in status since last imagingdrug testing may be conducted using urine, blood, or oral fluid, per standard of careremoved VAS, NOSE, and drug screen from the Implant visitconfirm urine pregnancy test completed within 2 weeks prior to implant, per standard of care	[REDACTED] Pr. CRS
3.0	
Amendment 2 includes the following updates:
 
Transitioned to 056-F275 CIP template vBUpdated language on study follow-up duration to include study exit at 6 months throughout (removal of 9 Month and 12 Month visits)[REDACTED]Entered final enrollment number of 93 subjects throughoutInserted Section 8: Study Site Requirements in alignment with new CIP TemplateUpdated section 10.5 (Post-Op) to include "Initial and Final device interrogation reports" missed under V2.0Updated section 10.1, Table 2, section 10.7, and section 10.11 (Table 3) to remove reference to 9 and 12 month visits[REDACTED][REDACTED]Updated language in section 14.1.1 and 14.4.1 to correct the non-inferiority margin for VAS from 1 to 10 and to clarify sample size calculationsUpdated section references throughout CIP	[REDACTED] Sr. CRS

2.0	
Transferred content to new template (vB)Updated non-inferiority margin for Secondary Objective #1 to 10 from 1Added considerations due to COVID-19, including:
Exits and deviationsData handling of remote visits[REDACTED]Updated primary analysis for primary objectiveAdded explanation of differing follow-up duration for CIP v3Added analysis clarifications and minor edits throughout	[REDACTED] Principal Statistician

2. List of Abbreviations and Definitions of Terms

Abbreviation	Definition
AE	Adverse Event
ATC	Anatomical Therapeutic Chemical
[REDACTED]	[REDACTED]
CI	Confidence Interval
CIP	Clinical Investigational Plan
COVID-19	Coronavirus Disease 2019
DD	Device Deficiency
[REDACTED]	[REDACTED]
FCS	Fully Conditional Specification
IDDS	Intrathecal Drug Delivery System
IT	Intrathecal
MedDRA	Medical Dictionary for Regulatory Affairs
MI	Multiple Imputation
MME	Morphine Milligram Equivalents
NOSE	Numerical Opioid Side Effect
[REDACTED]	[REDACTED]
PFMS	Preservative-Free Morphine Sulfate
[REDACTED]	[REDACTED]

Abbreviation	Definition
AE	Adverse Event
PT	Preferred Term
SAE	Serious Adverse Event
SAP	Statistical Analysis Plan
SAS	Statistical Analysis Software
SOC	System Organ Class
[REDACTED]	[REDACTED]
TDD	Target Drug Delivery
VAS	Visual Analog Scale
WHO	World Health Organization

3. Introduction

This statistical analysis plan (SAP) is based on Version 3 of the Embrace TDD Study Clinical Investigational Plan (CIP). CIP v3.0 changed the last study visit from the 12-Month Visit to the 6-Month Visit. Some subjects will have follow-up in the study past the 6-Month Visit, and other subjects will not have follow-up through the 12-Month Visit due to being consented and exited under CIP v3.0. The SAP presents the details of the methods to be used to analyze and report the study results of the Embrace TDD study, protocol number MDT18026.

4. Study Objectives

4.1 Primary Objective

To characterize the proportion of subjects with Clinical Success at the 6-Month Visit based on changes in pain intensity using the Visual Analog Scale (VAS) and changes in opioid-related side effects using the Numerical Opioid Side Effect (NOSE) Assessment Tool.

Clinical Success is defined as any of the following (*refer to grid below with matching numbers*):

- 1) Reduced opioid-related side effects with equal pain
- 2) Reduced pain with equal opioid-related side effects
- 3) Reduced pain and reduced opioid-related side effects

Criteria for Clinical Success

Change from Baseline to the 6-Month Visit			Opioid-Related Side Effects (NOSE)		
			≥20% Increase	< ±20% Change	≥20% Reduction
Pain Intensity (VAS)	Worse	Equal	Better		
	≥20% Increase	Worse			
	< ±20% Change	Equal			1
Pain Intensity (VAS)	≥20% Reduction	Better		2	3

4.2 Secondary Objectives

1. To demonstrate pain intensity scores (VAS) at the 6-Month Visit is non-inferior to VAS at Baseline
2. To characterize the change in opioid-related side effect scores (NOSE) from Baseline to the 6-Month Visit
3. To characterize the proportion of subjects who eliminate systemic opioids through the 6-Month Visit

4.4 Safety Assessment

To characterize all systemic opioid weaning-related, device-related, IT drug-related, and procedure-related adverse events (AEs), all serious adverse events (SAEs) (regardless of relatedness), and device deficiencies (DD) for all subjects from enrollment until the subject exits.

5. Investigation Plan

5.1 Study Design

The purpose of the study is to assess pain control and opioid-related side effects following a route of delivery change from systemic opioid therapy to IT morphine therapy.

This is a prospective, multi-center, post market study with commercially available products to evaluate the pain control and opioid-related side effects following a route of delivery change from systemic opioid therapy to IT morphine therapy in subjects with chronic, intractable, non-malignant primary back pain with or without leg pain. The study will be conducted at approximately 15 study sites in the United States.

5.2 Study Measures

5.2.1 Efficacy Measures

5.2.1.1 Visual Analog Scale (VAS)

Pain will be assessed using VAS. The VAS is a 100 mm line, with "No pain" on the left side of the line and "Worst pain imaginable" on the right side of the line. Subjects will be asked to mark a line perpendicular to the VAS line that best describes their average pain in the last 24 hours.

5.2.2 Safety Measures

Subjects will be assessed from enrollment through the end of the study for AEs related to the following:

- Systemic opioid weaning
 - Device
 - IT drug
 - Procedure

In addition, all SAEs (regardless of relatedness) and device deficiencies reported during the study will be collected. All subject deaths (regardless of relatedness) must be reported to Medtronic.

5.2.3 Schedule of Events by Visit and Visit Windows

Study procedures and data collection requirements for the study are summarized in Table 5-1. The study visit windows for all the required study visits are provided in Table 5-2. The 9- and 12-Month Visits were required under CIP v1.0 and v2.0; they are not scheduled study visits under CIP v3.0.

Table 5-1 Schedule of Events by Visit

Study Procedures, Tasks, and Data Collection (row) by Visit (column)	Baseline Visit (Enrollment)	Intrathecal Trial Visit		Implant Visit	Post-Op Visit	IT Therapy Initiation	1-Month Visit	3-Month Visit	6-Month Visit	9-Month Visit ¹	12-Month Visit ¹	Unscheduled Visits
		IT	Implant									
Informed Consent Process	✓											
Demographics	✓											
Inclusion/Exclusion Criteria	✓	✓										
Urine Pregnancy Test	✓	✓	✓ ²			✓	✓	✓	✓	✓	✓	
Drug Test	✓	✓				✓	✓	✓	✓	✓	✓	
Adjunctive pain management therapies	✓	✓	✓			✓						
Back and Leg Pain/Surgical History	✓											
VAS	✓	✓				✓	✓	✓	✓	✓	✓	
NOSE Assessment	✓	✓				✓	✓	✓	✓	✓	✓	
IT PFMS Dose						✓	✓	✓	✓	✓	✓	
Fluoroscopy/x-ray			✓									
Device information (model, serial/lot #)			✓									
Drug information (name, lot #/identifier, dose & concentration)		✓				✓	✓	✓	✓	✓	✓	
Initial and final device interrogation reports			✓	✓	✓	✓	✓	✓	✓	✓	✓	
Collect AEs/DDs	✓ ³	✓	✓ ³	✓	✓	✓	✓	✓	✓	✓	✓	
Pain Medications	✓	✓	✓	✓	✓	✓	✓	✓	✓	✓	✓	

¹Required visits under CIP v1.0 and v2.0, not required under CIP v3.0.

²Confirm pregnancy test completed within 2 weeks prior to implant visit

³Device Deficiencies will be collected and reported from the Implant Visit through the 12-Month Visit/Study Exit

Table 5-2 Visit Windows

Study Visits	Visit Windows	
Baseline Visit	Date of Enrollment (Date ICF/HIPAA signed and dated)	
Intrathecal Trial Visit	After Baseline and prior to Implant	
IT Therapy Initiation (Day 0) Implant to Post-Op Visit	Implant Visit	≤150 days after the Baseline Visit
	Post-Op Visit	14 ± 4 days after the Implant Visit
	1-Month Visit	30 days ± 5 days after Day 0
	3-Month Visit	90 days ± 10 days after Day 0
	6-Month Visit ¹	180 days ± 10 days after Day 0
	9-Month Visit ²	270 days ± 15 days after Day 0
	12-Month Visit (Study Exit) ²	360 days ± 15 days after Day 0

¹ Study Exit Visit under CIP v3.0² Required Visits under CIP v1.0 and 2.0

[figure not shown]
6. Determination of Sample Size

Approximately 100 subjects will be enrolled into the study to get a minimum of 67 implanted subjects and at least 50 evaluable subjects at the 6-Month Visit. The sample size of 50 evaluable subjects was chosen to assure acceptable levels of precision for estimation of the primary objective of Clinical Success and provide adequate power to test the secondary objective related to pain score.

There were no available data in the target population on the primary objective of Clinical Success, nor on the secondary objective of opioid-related side effects score. The secondary objective of pain intensity score is used for sample size calculation. It is hypothesized that the pain intensity score of VAS at the 6-Month Visit is non-inferior to those at Baseline using a non-inferiority approach.

The PASS 11 Non-Inferiority Tests for One Mean was used to calculate the power for pain intensity of VAS with the following assumptions: Sample size = 50, Alpha = 0.025, Non-Inferiority Margin = 1, True Difference = 0, Standard Deviation = 1.9, with Higher Means are Worse (one-sided) t-test. A sample size of 50 would achieve 95% power with the above assumptions. This power calculation was performed using a pain scale of 0-10; however, the power calculation is identical to one with a non-inferiority margin of 10 and assuming a standard deviation of 19 on a VAS pain scale of 0-100.

The non-inferiority margin of 10 points was chosen based on a review of pain study literature. Non-inferiority margins between 1 and 1.5 were reported for pain scales of 0-10, including one study in a similar population of chronic non-malignant pain subjects comparing 2 oral opioids that utilized a margin of 1.¹ The estimated actual difference was assumed to be 0 because the goal is to achieve same or better pain control as compared to Baseline.

The non-inferiority margin of 1 on a pain scale of 0-10 is equivalent to a non-inferiority margin of 10 on a VAS pain scale of 0-100.

A 33% attrition between enrollment and subject implant is assumed and a 25% attrition between Implant and the 6-Month Visit is assumed. To achieve at least 50 evaluable subjects at the 6-Month Visit, a minimum of 67 subjects are required to be implanted and approximately 100 subjects to be enrolled.

The 33% attrition between enrollment and subject implant accounts for the subjects who don't meet inclusion and/or exclusion criteria, those who can't follow the weaning process to eliminate systemic opioids, those who don't have a successful IT trial, those who have adverse events that can no longer be followed in the study, withdrawals, and lost-to-follow-up, etc. The attrition between implant and the 6-Month Visit is conservatively set at 25% to potentially account for the subjects who have adverse events that can no longer be followed in the study, withdrawals, are lost-to-follow-up, or subjects who can't be effectively managed on morphine monotherapy.

7. Statistical Methods

7.1 Study Subjects

7.1.1 Disposition of Subjects

Subject disposition will be summarized using a flow diagram. Reasons for subject discontinuations, including those due to COVID-19 and/or the pump supply shortage, will be summarized.

7.1.2 Clinical Investigation Plan (CIP) Deviations

All CIP deviations will be summarized by type of deviation. Details of CIP deviations that affect scientific integrity or patient safety will be presented. Additionally, separate summaries of study deviations due to COVID-19 and due to the pump supply shortage with their respective impact on the study data will be provided.

7.1.3 Analysis Sets

Full Analysis Set

All enrolled subjects will be included in the Full Analysis Set. This data set is also used for safety analysis, as well as for the analysis of systemic opioids weaning and holiday process.

IT Trial Analysis Set

All subjects who experience the IT trial will be included in the IT Trial Analysis Set.

Implanted Analysis Set

All subjects who are implanted with the Intrathecal Drug Delivery System (IDDS) will be included in the Implanted Analysis Set. This data set is used for supporting analysis for the primary and secondary objectives, as well as the analysis of adverse events that are related to device, IT drug, and procedure, and device deficiencies.

Completers Analysis Set

The implanted subjects who provide data at both the Baseline and the 6-Month Visit will be included in the Completers Analysis Set. This data set is used for supporting analysis for the primary and secondary objectives, as well as some additional measures at the 6-Month Visit. Completers Analysis Set may vary for different measures based on the subjects who provide data.

Per-protocol Analysis Set

The implanted subjects who maintain morphine monotherapy and provide data at both the Baseline and the 6-Month Visit will be included in the Per Protocol Analysis Set. This data set is used for a supporting analysis for the primary objective and the primary analyses for the secondary objectives, as well as some additional measures at the 6-Month Visit. Per-protocol Analysis Set may vary for different measures based on the subjects who provide data.

Primary Objective Analysis Set

The implanted subjects who maintain morphine monotherapy and provide data at both the Baseline and the 6-Month Visit through the date of the snapshot that will be conducted in November 2021 will be included in the Primary Objective Analysis Set. This data set is used for primary analysis for the primary objective. This analysis set may be a subset of subjects in the Per-Protocol and Completers Analysis Sets, as additional subjects may complete their 6-Month Visit following the November 2021 snapshot.

Long-term Analysis Sets

The implanted subjects who provide data at both the Baseline and the 12-Month Visit will be included in the Long-term Analysis Sets. These analysis sets include both per-protocol population (who maintain morphine monotherapy throughout the 12-Month Visit) and completers population.

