10.1 Summary of Visits

Study procedures and data collection requirements for the study are provided in detail below for each visit and summarized in Table 3: Schedule of Events within Section 10.11. Refer to Section 6, Figure 1: Embrace TDD Study Visit Flowchart for a diagram of the required study visits.

A summary of the required visits are as follows:

- Baseline Visit
- Intrathecal Trial Visit
- Implant Visit
- Post-Op Visit
- 1-Month Visit
- 3-Month Visit
- 6-Month (Study Exit) Visit

Table 2: Visit Windows provides details regarding the study visit windows for all required study visits.

Table 2: Visit Windows

Study Visits	Visit Windows	
Baseline Visit	Date of Enrollment (Date ICF/HIPAA signed and dated)	
Intrathecal Trial Visit	After Baseline and prior to Implant	
IT Therapy Initiation (Day 0) Implant to Post-Op Visit	Implant Visit	≤ 150 days after the Baseline Visit
	Post-Op Visit	14 ± 4 days after the Implant Visit
	1-Month Visit	30 days ± 5 days after Day 0
	3-Month Visit	90 days ± 10 days after Day 0
	6-Month Visit (Study Exit)	180 days ± 10 days after Day 0

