10.3 Intrathecal Trial Visit

Site personnel must ensure the subject meets eligibility criteria prior to initiating any IT drug trial procedures. Subjects will be asked to complete the VAS for pain intensity and the NOSE assessment tool. The investigator must then confirm the subject's systemic opioid dose is \leq 60 MME prior to moving forward with the IT drug trial. Females of child-bearing potential (not post-menopausal or surgically sterile) must be administered a urine pregnancy test at this visit to confirm they are not pregnant. In addition, site personnel must confirm each subject's drug testing results for systemic opioids and confirm results are negative for cannabinoids and illicit drugs. If it is determined the subject no longer meets eligibility criteria, or they choose to withdraw early, the subject will be exited from the study according to Section 10.10.

The IT trial will be conducted according to the investigator's standard of care procedures. A successful IT trial will be determined by the investigator and documented accordingly.

If the investigator determines the IT trial was not successful, the subject will be considered a screen failure and will be exited from the study according to Section 10.10.

Data Collection Requirements for the IT Trial Visit:

- Inclusion/exclusion criteria
- VAS
- NOSE
- Adjunctive pain management therapies utilized
- Urine pregnancy test results, if applicable
- Drug testing results for systemic opioids, cannabinoids, and illicit drugs
- Date systemic opioids were stopped, if prior to trial
- IT trial method, drug name, lot number/identifier, dose(s) and concentration(s)
- Pain medications
- AEs

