Malfunction: (ISO 14155:2011 3.27)	
Failure of an investigational medical device to perform in accordance with its intended purpose when used in accordance with the instructions for use or (CIP).

Use Error: (ISO 14155:2011 3.43)	
Act or omission of an act that results in a different medical device response than intended by the manufacturer or expected by the user.
 
NOTE 1: Use error includes slips, lapses, and mistakes.
 
NOTE 2: An unexpected physiological response of the subject does not in itself constitute a use error.

Term	Seriousness
Serious Adverse Event (SAE): (ISO 14155:2011 3.37)	
Adverse event that
 
 a) led to death, b) led to serious deterioration in the health of the subject, that either resulted in 
 1) a life-threatening illness or injury, or 2) a permanent impairment of a body structure or a body function, or 3) in-patient or prolonged hospitalization, or 4) medical or surgical intervention to prevent life-threatening illness or injury or permanent impairment to a body structure or a body function, c) led to fetal distress, fetal death or a congenital abnormality or birth defect. 
NOTE: Planned hospitalization for a pre-existing condition, or a procedure required by the CIP, without serious deterioration in health, is not considered a serious adverse event.

Term	Definition
Serious Adverse Device Effect (SADE): (ISO 14155:2011 3.36)	Adverse device effect that has resulted in any of the consequences characteristic of a serious adverse event
Term	Relatedness
Systemic Opioid Weaning-Related	An adverse event related to the systemic opioid weaning process (i.e. opioid-related withdrawal symptoms)
Device-Related	An adverse event that results from the presence or performance (intended or otherwise) of the SynchroMed II infusion system.
IT Drug-Related	Event related to the IT drug delivered by the device. Normally IT drug-related events resolve when the device is turned off or reprogrammed, or the drug is removed from the pump. This category should not include events that resulted from a malfunction of the device (i.e. hardware-related events).
Procedure-Related	An adverse event that occurs due to any procedure related to the IT trial, implant, pump refills, programming, or surgical modification of the system.

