12.2 Reporting of Adverse Events

Any AE meeting the definition of systemic opioid weaning-related, device-related (i.e. SynchroMed II infusion system), IT drug-related, and procedure-related (i.e. IT trial, implant or pump refill/reprogramming, system modification), and all serious adverse events and deaths (regardless of relatedness), for all subjects from the Baseline Visit through study exit will be collected.

It is the responsibility of the investigator to identify the occurrence of any reportable adverse events and to ensure all required information is accurately recorded in the subject's medical record and reported to Medtronic on an event eCRF. IRB reporting must be completed in accordance with the policies of the governing IRB. Refer to the eCRF for the information to be reported for each AE.

For AEs that require immediate reporting, initial reporting to Medtronic may be done by phone, fax, or e-mail, or on the eCRF by completing as much information as is available. The AE eCRF must be completed as soon as possible.

In case the investigator requires information from the sponsor in an emergency, the investigator can contact Medtronic using the contact details provided in the synopsis and Section 12.5.

The clinical course of each AE must be followed until the adverse event is resolved, the subject is in a stable condition, or until the subject discontinues from the study. "Ongoing" AEs must be assessed at each study visit. The AE eCRF should be updated when there is a change to the information provided on the form (e.g. change in intervention, outcome, relatedness, etc.).

At the last study visit, the investigator will instruct the subject to provide an update on the status of any ongoing events and report any AE they believe may be related to participation in the study.

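### SAP 7.1.3 places procedure-related adverse events on the Implanted Analysis Set, so a table on that set omits IT-trial complications in subjects who were trialled but never implanted

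*SAP*

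**What the plan says.** SAP 7.1.3 defines the Implanted Analysis Set as the subjects who receive the implanted system. It gives that set several uses, one of which is "the analysis of adverse events that are related to device, IT drug, and procedure, and device deficiencies". The same section says of the Full Analysis Set, which holds all enrolled subjects, "This data set is also used for safety analysis". It also defines an IT Trial Analysis Set of everyone who undergoes the trial.

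Protocol 12.1 (Table 4) defines a procedure-related event as "An adverse event that occurs due to any procedure related to the IT trial, implant, pump refills, programming, or surgical modification of the system". Protocol 12.2 repeats the scope: "procedure-related (i.e. IT trial, implant or pump refill/reprogramming, system modification". Protocol Table 2 times the IT trial as "After Baseline and prior to Implant". Protocol 10.3 says what follows a failed trial: "If the investigator determines the IT trial was not successful, the subject will be considered a screen failure and will be exited from the study".

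SAP 7.10 and protocol 14.6 both set the safety scope, procedure-related events included, as every subject from enrolment to exit. SAP 7.10 promises event counts and the number and percentage of subjects affected, categorised by relatedness. It names no analysis set for any of these tables. Protocol 13 says that incidence rates will be tabulated from the events committee's determinations.

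**The concern.** A complication of the IT trial is procedure-related by the protocol's own definition. If the subject is never implanted, the event lies outside the set that SAP 7.1.3 names for procedure-related events. A programmer who follows 7.1.3 leaves that subject out of both numerator and denominator. One who follows the scope statement in 7.10 includes the subject. The SAP does not say which of the two gives the percentage in the relatedness table.

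The choice matters because entry to the Implanted set depends on what happens at the trial. A complication serious enough to prevent implant removes its own subject from the table. The resulting percentage describes trial risk only in those who went on to implant, which is not the question asked by someone deciding whether to undergo a trial.

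**Working it through.** **1. Set membership.** An IT-trial complication in a subject never implanted is procedure-related (protocol 12.1, 12.2), occurs before implant (Table 2), and belongs to a subject in the Full and IT Trial sets but not in the Implanted set (SAP 7.1.3). The omission follows from the definitions and needs no numbers.

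**2. How many subjects could be affected.** The plan's attrition chain reproduces: 50/(1 − 0.25) = 66.7, rounded up to 67 implanted; 67/(1 − 0.33) = 100 enrolled (SAP 6). The number never implanted is then:
- SAP plan: 100 − 67 = 33.
- Protocol 14.1.1, 93 enrolled and about 67 implanted: 93 − 67 = 26.
- 33% attrition applied to 93: 93 × 0.67 = 62.3, so about 62 implanted and 31 not.

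These are ceilings for k, the number trialled but not implanted. Pre-implant attrition in SAP 6 includes subjects who do not "have a successful IT trial, those who have adverse events that can no longer be followed in the study", but also those who cannot "follow the weaning process to eliminate systemic opioids", and the latter may leave before any trial. The documents do not give k.

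**3. Effect on the count.** Let x be the number of implanted subjects with a procedure-related event and y the number of trialled, never-implanted subjects with one. The Implanted set gives x and all trialled subjects give x + y. Since y ≥ 0, the count on the Implanted set can only be too low.

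**4. Effect on the percentage.** With 67 implanted, the Implanted set gives x/67 and all trialled subjects give (x + y)/(67 + k). Never-implanted subjects cannot have implant, refill or system-modification events. Adding them therefore dilutes the percentage unless their trial-event rate is high enough to offset this.

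Illustration, every value assumed: x = 10, a trial-event rate of 5% in implanted subjects, and a rate in the never-implanted that is RR times as high, so y = k × 0.05 × RR. The Implanted set gives 10/67 = 14.9% throughout. With k = 10 and 77 trialled:
- RR = 1: (10 + 0.5)/77 = 13.6%
- RR = 2: (10 + 1.0)/77 = 14.3%
- RR = 4: (10 + 2.0)/77 = 15.6%

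The same formula for other k:

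| k | Trialled | RR = 1 | RR = 2 | RR = 4 |
|---|---|---|---|---|
| 5 | 72 | 10.25/72 = 14.2% | 10.5/72 = 14.6% | 11/72 = 15.3% |
| 10 | 77 | 13.6% | 14.3% | 15.6% |
| 26 (ceiling) | 93 | 11.3/93 = 12.2% | 12.6/93 = 13.5% | 15.2/93 = 16.3% |

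The two percentages agree when y/k = 10/67 = 14.9%, which is RR = 14.9/5, about 3. Below that the Implanted set gives the higher figure, and above it the lower.

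**5. Full Analysis Set as denominator.** With k = 10 and RR = 1, 2 and 4, the figures on 93 enrolled are 10.5/93 = 11.3%, 11/93 = 11.8% and 12/93 = 12.9%. They are diluted by subjects who had no procedure at all.

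**The case against.** The best defence is that the SAP already covers these events. The Full Analysis Set is named for safety, and 7.10 opens with an all-subject scope before it turns to relatedness. On that reading the relatedness tables run on all subjects, and 7.1.3 merely adds an implanted-only analysis. Safety is also purely descriptive, with no test or decision attached, and sampling error is far larger than the shift: 3 affected subjects of 67 (4.5%) has an exact 95% interval of about 0.9% to 12.5%.

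Much of this stands. It limits the consequence to one table and makes the point minor. It does not remove the explicit assignment in 7.1.3, and 7.10 still does not say which set supplies the percentage.

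Three stronger readings are tempting, and the documents support none of them.
- A reader might infer that trial complications vanish from the report. The Full Analysis Set's safety use and the scope of 7.10 say otherwise.
- A reader might infer that the Implanted-set percentage must understate procedural risk. It need not, as the dilution at RR of 1 and 2 shows. Subjects who missed implant for unrelated reasons, such as the pump supply shortage mentioned in SAP 7.1.1, would pull RR towards 1.
- A reader might infer that the IT Trial Analysis Set was defined and then left unused. SAP text just before 7.10 is blacked out and may give it a use.

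**Conclusion.** The point holds as a mis-assigned analysis set for one class of adverse event. As written, SAP 7.1.3 puts procedure-related events on a set that excludes some subjects exposed to a protocol-defined procedure, contrary to the all-subject scope of SAP 7.10 and protocol 14.6. Only the procedure-related count and percentage are affected. The direction for the count is certain, because it can only be understated. The direction for the percentage is not: in the illustration the figure on all trialled subjects runs from 1.3 points below the Implanted-set figure to 0.7 above it at k = 10, and from 2.8 below to 1.4 above at the ceiling of k = 26. Those sizes rest wholly on assumed values of x, k, the 5% rate and RR. The set-membership argument rests on readable text alone. Severity: minor.

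**What to change.** Amend SAP 7.1.3 and 7.10 so that each related-event table names its set and denominator:
- IT-trial procedure-related events: IT Trial Analysis Set.
- Procedure-related events from implant onward, device-related events, IT drug-related events and device deficiencies: Implanted Analysis Set. IT drug-related events belong here because protocol Table 4 ties them to drug delivered by the device. A sentence should say so, since drug is also given at the trial.
- All procedure-related events: counted in the overall Full Analysis Set summary.

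The cost is wording in two SAP sections and an added table. No new data are needed, because protocol 12.2 already collects these events from Baseline and the IT Trial Analysis Set is already defined. The downside for the sponsor is a procedure-related count that may be higher.
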